14 STATISTICAL METHODS

14.1 Sample Size

To answer study primary objective, this chart review study plans to accrue a minimum of 60 study eyes that have had at least 3 years of follow-up data without a SSI for glaucoma after the initial implant with XEN 45 Gel Stent.

Data from the Allergan study MS-001 demonstrated that the mean IOP reduction from baseline differed slightly among the 7 visits (see below) in the 24-month post-implant period. The absence of a clear waning-out trend suggests that the effect of XEN 45 Gel Stent implantation on IOP reduction may last to Month 36 and beyond. The minimum mean reduction (negative sign stands for reduction) in IOP among the visits was -5.6 (± 6.32) mmHg, which was observed at Month 3. This value was then taken as an initial estimate for the mean reduction projected for Month 36. The 95% confidence interval (CI) of the projected mean reduction afforded by a sample of 60 study eyes is -7.2 to -4.0 mmHg. That is, the half-length of the interval is 1.6 mmHg, which provides a reasonable precision for the estimate of the projected mean reduction in IOP.

Table 4 Result from the MS-001 Study

Visit	Number of study eyes	Mean (SD) change in IOP from medicated baseline (mmHg)
Month 1	167	-6.3 (6.41)
Month 3	167	-5.6 (6.32)
Month 6	168	-6.4 (4.92)
Month 9	134	-6.1 (5.68)
Month 12	161	-6.7 (5.41)
Month 18	149	-7.1 (5.10)
Month 24	149	-6.2 (4.94)

The MS-001 study enrolled 199 patients (218 study eyes). In this study, patients' discontinuation rate tended to be linear over the 2-year follow-up period, with an overall study discontinuation rate of approximately 20%. Using data from the MS-001 study, it could be assumed that 30% of the eyes selected for this study have less than 3 years of follow-up data. Taking into consideration that MS-001 study was a clinical trial and that patient retention rate is expected to be lower in a real-world setting, the study will aim to select 150 eyes to ensure obtaining a minimum of 60 eyes with at least 3 years of follow-up data.

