14.2.1 Study Populations and Analysis Methods

- Analysis Population: all eyes selected and meeting the selection criteria.
- Subgroups analyses will be conducted in eyes that did or did not undergo phacoemulsification. Additional subgroups may be further considered in the SAP.

Continuous variables will be described by their mean, standard deviation, median, upper and lower quartiles, extreme values (minimum and maximum) and the number of missing data.

Categorical variables will be described by the number and percentage of each response and the number of missing data.

Figures will be generated, when appropriate, to describe change in parameters over time.

Some of the data will only be collected if they occurred within study-defined time windows (see Section 7.2). Since all data within the defined time windows will be collected, more than one value could be available per time window for a given parameter. Rules to determine which value will be used for the analysis will be defined in the SAP.

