14.2.4 Primary Objective

Change in IOP from medicated baseline and change in the number of topical IOP-lowering medications compared to baseline will be summarized descriptively at Year 3 after XEN 45 Gel Stent implantation in eyes from the Analysis Population with at least 3 years of follow-up data and were not treated with Diamox on the day when decision was taken to implant XEN 45 Gel Stent.

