 - Persistent corneal decompensation / edema (>30 days)
 - Mild corneal decompensation / edema

[figure not shown]

-
- Moderate corneal decompensation / edema
 - Severe corneal decompensation / edema
 - Cyclodialysis
 - Endophthalmitis
 - Hyphema
 - ≥ 2 mm in height (layered) at any time; present or arising > 30 days postoperatively
 - Persistent hypotony: IOP < 6 mmHg, present at two consecutive visits postoperatively > 30 days apart
 - Clinical hypotony: vision reduction (2 lines or more) related to macular changes consistent with hypotony maculopathy (macular folds), optic disc edema, and/or serious choroidal detachments because of low IOP
 - Implant blockage in the anterior chamber
 - Implant exposure or extrusion
 - Implant fracture
 - Implant migration
 - Implant repositioning requiring surgical intervention
 - Implant touching iris
 - Implant touching cornea
 - Iridodialysis
 - Iritis (requiring treatment after the postoperative medication taper)
 - Macular edema
 - Ptosis
 - Retinal detachment
 - Suture abscess or other local infection
 - Vitreous hemorrhage
 - Any other adverse event that leads to permanent visual impairment or requires surgical or medical intervention to prevent permanent visual impairment

2. Sample Size

A sample size of 150 patient eyes was selected, as it is anticipated that this will allow for the inclusion of a minimum of 60 independent study eyes have at least 3 years of follow-up data without a SSI for glaucoma after the initial implant with XEN 45 Gel Stent. Based on the Allergan study MS-001, for month 36 the 95% confidence interval (CI) of the projected mean IOP reduction afforded by a sample of 60 study eyes is -7.2 to -4.0 mmHg. That is, the half-length of the interval is 1.6 mmHg, which provides a reasonable precision for the estimate of the projected mean reduction in IOP.

3. Data Handling

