3.4. Missing Data

The eCRF is designed to ensure that no questions are left unanswered. If 'unknown' is selected, this will be included as such in the results and tabulated for all variables. Central tendencies will not be measured for continuous unknown data, only counts and percentages will be recorded.

In some cases, imputation of unknown variables may be conducted if the variable is to be used in calculations for another variable or analysis. For example, the eCRF allows some dates to be incomplete (i.e. day is unknown) if it is not available in the medical chart. This may impact accurate calculation of durations, resulting in an imputation needing to be made. If the day is missing, the date will be imputed as the 15th of the month, except in cases where this would lead to a negative duration, in which case the 1st or last day of the month will be used (whichever addresses the negative duration). No imputation will be made for missing month/year; these are classified as date unknown within the eCRF. All imputed values will be documented and presented as footnotes in the result tables.

4. Planned Analyses

The analyses detailed below will be performed to meet the project objectives. There will be two analysis populations specified for the analyses to be conducted:

- The **Effectiveness Population** consists of all eligible study eyes in the population except in instances when a patient has contributed both eligible eyes in the study, then only the eye that received the Xen-45 implant first will be selected; this eye will be presented in tables as the 'primary eye'. All results tables in the Effectiveness Population will include stratified results presenting data for the primary eye, as well as data on all included patient eyes (even if both eyes from a single patient are included).
- The **Safety Population** consists of all eligible study eyes in the population.

All results tables will be stratified by Xen-45 implant only, implant plus phacoemulsification, and total population. Sensitivity analyses will be conducted to assess study results in the 'second eye' (i.e. not the primary eye as described above), for patients where both eyes were included. The sensitivity analyses will focus on the tables conducted using the Effectiveness Population.

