Categorical variables will be summarised by number and percentage of each response and will include number of unknown responses. Continuous variables will be summarised by mean, standard deviation, median, upper and lower quartiles, minimum and maximum values and proportion with unknown data.

[figure not shown]

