These will be compared to baseline and will be summarised descriptively at months 12, 24, 36 and 48 after XEN 45 Gel Stent implantation in eyes from the Effectiveness Population. Analyses will only include those with available data at each of the time points of interest and those who were not treated with Diamox on the day when decision was taken to implant XEN 45 Gel Stent.

A paired t-test will be applied for statistical analysis in comparing the difference between post baseline to baseline values. The assumptions of the test are as follows:

- No significant outliers in the differences between time points (which can be tested by a scatter plot of the data)
- The distribution of the differences in the dependent variable between the two time points should approximately follow a normal distribution (which can be tested through the Shapiro-Wilk test)
- The dependent variable is measured on a continuous scale

If the assumptions of the t-test are heavily violated then the non-parametric analogue (Wilcoxon Signed-Rank test) should be used to test the difference between time points.

4.4.1. Success over the long term of following implantation of the XEN 45 Gel Stent

Number and proportion of eyes achieving a 20% reduction in IOP from medicated baseline, and number and proportion of eyes with an IOP between 6 and 18 mmHg, IOP between 6 and 17 mmHg, ..., down to IOP between 6 and 12 mmHg will be described by the time-windows described in Section 4.1 in eyes from the Effectiveness Population that did not undergo SSI for glaucoma, and were not treated with Diamox on the day when decision was taken to implant XEN 45 Gel Stent.

The number and proportion of eyes achieving qualified or complete success at each time point of interest (i.e. 12, 24, 36, 48 and >51 months) after XEN 45 Gel Stent implantation will be summarised descriptively. Analyses will be conducted in the Effectiveness Population.

The time from XEN 45 Gel Stent implantation to SSI for glaucoma will be described using Kaplan Meier curves.

4.5. Safety over the long term following implantation of the XEN 45 Gel Stent

Surgical complications and post-operative AESIs will be summarised descriptively using frequencies and percentages.

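### The study is sized only on the width of a 95% CI, but the analysis plans no CI, and the planned t-test would ignore fellow-eye correlation if applied to the required all-eyes results

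*SAP*

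**What the plan says.** **Sizing.** Protocol 14.1 takes the MS-001 Month 3 result, a mean change of -5.6 mmHg with SD 6.32, as the projection for Month 36. For 60 eyes it gives a 95% CI of -7.2 to -4.0 mmHg and concludes that "the half-length of the interval is 1.6 mmHg, which provides a reasonable precision". SAP 2 repeats the argument, refers to "the 95% confidence interval (CI) of the projected mean IOP reduction afforded by a sample of 60 study eyes", and specifies that the 60 eyes are independent. Neither document gives a hypothesis, a significance level or a power.

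**Analysis.** Under Protocol 14.2.4 the primary outcomes "will be summarized descriptively at Year 3 after XEN 45 Gel Stent implantation in eyes from the Analysis Population". The summary statistics are listed in Protocol 14.2.1 ("Continuous variables will be described by their mean, standard deviation, median, upper and lower quartiles, extreme values (minimum and maximum", plus the number missing) and in SAP 4 ("Continuous variables will be summarised by mean, standard deviation, median, upper and lower quartiles, minimum and maximum values and proportion with unknown data"). Neither list contains a CI. SAP 4.4 adds the only inference on change: "A paired t-test will be applied for statistical analysis in comparing the difference between post baseline to baseline values". The fallback is "If the assumptions of the t-test are heavily violated then the non-parametric analogue (Wilcoxon Signed-Rank test) should be used".

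**Bilateral eyes.** SAP 1.6 refers the reader to section 4. There the Effectiveness Population takes the first-implanted eye of a bilateral patient as the primary eye. The same bullet then says "All results tables in the Effectiveness Population will include stratified results presenting data for the primary eye", together with results for every included eye, both eyes of one patient among them. A sensitivity analysis covers second eyes. No method for correlated fellow eyes is named.

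**The concern.** There are two separate gaps.

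First, precision is the only design property the study claims, and the planned output does not state it. The planned test does not replace it: a comparison with baseline in treated eyes, at the projected effect, will give a small p-value whether or not the three-year change is precisely estimated.

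Second, SAP 4.4 places its analyses in the Effectiveness Population, and every table for that population has an all-eyes version. The section does not say whether the test is run there. Pairing in that test means baseline against follow-up in the same eye, which does nothing for the correlation between two eyes of one patient. The listed test assumptions cover outliers, normality and a continuous scale, but not independence of eyes. If the test is run on all eyes, or a reader builds an interval from the all-eyes mean, SD and n, the error bar is too narrow, and it appears beside the valid primary-eye result.

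**Working it through.** **Inputs.** Mean change -5.6, SD 6.32 and n = 60 (Protocol 14.1; SAP 2). MS-001 enrolled 218 eyes in 199 patients (Protocol 14.1). The documents do not give the fellow-eye correlation of the IOP change, rho; 0.3 to 0.7 is assumed. They do not give this study's bilateral share either.

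**1. The plan's own figure.** Half-length = 1.96 × SD / √n = 1.96 × 6.32 / √60 = 1.599, so the interval is -7.20 to -4.00. Solving for n: (1.96 × 6.32 / 1.6)² = 59.9, hence 60. The stated figures reproduce. With the t quantile on 59 df the half-length is 1.633 (-7.23 to -3.97).

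**2. What the t-test can show.** Taking a two-sided 5% level (the SAP states none), at n = 60 and SD 6.32 any mean reduction above 1.63 mmHg is significant. The projection is 5.6. The standard error is 6.32 / √60 = 0.816, so the noncentrality is 5.6 / 0.816 = 6.9 and power exceeds 0.9999.

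**3. Fellow eyes in the all-eyes results.** MS-001 had 218 - 199 = 19 bilateral patients, so a share f = 38/218 = 17.4% of eyes belong to a pair. Treating eyes as independent omits a design effect of 1 + f × rho. The standard error is too small by 1 - 1/√(design effect), and the true two-sided error is 2 × (1 - Φ(1.96/√(design effect))).

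| f | rho | Design effect | SE too small by | True error at nominal 5% |
|---|---|---|---|---|
| 17.4% | 0.3 | 1.052 | 2.5% | 5.6% |
| 17.4% | 0.5 | 1.087 | 4.1% | 6.0% |
| 17.4% | 0.7 | 1.122 | 5.6% | 6.4% |
| 50% (assumed) | 0.3 | 1.15 | 6.7% | 6.8% |
| 50% (assumed) | 0.5 | 1.25 | 10.6% | 8.0% |
| 50% (assumed) | 0.7 | 1.35 | 13.9% | 9.2% |

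**4. The same in mmHg.** Sixty patients at the MS-001 ratio give 60 × 218/199 = 65.7, say 66 eyes: 54 single eyes and 6 pairs. Treated as independent, the half-length is 1.96 × 6.32 / √66 = 1.525. Allowing for pairing it is 1.96 × 6.32 × √(66 + 12 × rho) / 66 = 1.566, 1.593 or 1.619 for rho 0.3, 0.5 or 0.7. The primary-eye half-length is 1.599.

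**The case against.** The best defence is that SAP 4 defines the Effectiveness Population with one eye per patient, so a test in that population is a primary-eye test, and the all-eyes sentence only asks for data to be presented. First-eye selection with a separate second-eye analysis is a sound way to handle bilateral eyes, and it matches the 60 independent eyes of SAP 2. This stands for the primary-eye result, which is valid. It does not settle the all-eyes results: the bullet that selects one eye also requires all eyes in every Effectiveness table, and SAP 4.4 does not say that the test is omitted there.

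The defence is also right that the CI can be rebuilt from mean, SD and n, so its absence is mainly a reporting gap. A rebuilt mean-based interval would not correspond to the Wilcoxon test, however, if that fallback is used. Finally, SAP section numbers go from 4.6 to 7 in the text available, so the absence of a CI can be stated only for what is visible.

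A reader might infer three stronger things that the documents do not support:

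- **The analysed n will fall below 60.** SAP 2 counts eyes with three years of follow-up and no SSI, while SAP 4.4 analyses eyes with data in the Month 36 window and no Diamox on the decision day. These sets differ, but the difference could go either way. Protocol 7.1 continues extraction until the target for the primary analysis is met. With the 30% loss that Protocol 14.1 derives from MS-001, 150 eyes are 150 × 199/218 = 136.9 patients, of whom 95.8 remain. Assumed further losses of 10% to 30% leave 86 to 67, with half-lengths of 1.34 to 1.51 mmHg, inside 1.6. The protocol expects poorer retention than MS-001, so this does not prove that 60 is reached, but no shortfall is shown.
- **The extra precision of the all-eyes results is wholly spurious.** That depends on rho. In the 66-eye example, at rho 0.3, (1.599 - 1.566) / (1.599 - 1.525) = 45% of the apparent gain is real; at 0.5 almost none is.
- **The sample size is wrong.** It reproduces.

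**Conclusion.** The point holds as a modest one. Precision is the sole sizing criterion, and no CI appears in the visible analysis text of either document. For the primary eye this costs the reader a short calculation and no validity. For the all-eyes results, inference as written would treat fellow eyes as independent, with a small effect: a true error of 5.6% to 6.4% at the MS-001 share, and 6.8% to 9.2% if half the eyes were paired. Both ranges assume rho between 0.3 and 0.7. The MS-001 share is borrowed and need not be an upper limit, because Protocol 9.2 brings in an eligible second eye out of chronological order. No formal decision rests on the test, and at the projected effect no conclusion would change. What is affected is an error bar. The amendment is worth making because it is nearly free and makes the report show the one property on which the study was designed.

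**What to change.** In SAP 4.4:

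1. Report the Month 36 mean IOP change in the primary eye with its two-sided 95% CI, beside the test. If the Wilcoxon test is used, add the Hodges-Lehmann estimate with its 95% CI. Do the same for the change in number of topical medications, the other half of the primary objective.
2. For any all-eyes test or interval, use patient-clustered standard errors or a model with a patient random effect, using the eye pairing already held in the EDC. Alternatively, state that the all-eyes results are descriptive only and carry no test or interval.

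No separate restatement of the 1.6 mmHg is needed, since the reported CI shows the precision at the n and SD actually analysed. The cost is a few lines of SAP text and minor programming, with no new data or chart extraction. The downside is slightly wider all-eyes intervals.

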3.1. Raw Datasets

The raw database generated in Dacima, containing all completed eCRFs will be exported directly into SAS.

3.2. Derived Datasets

Analysis will be conducted on derived datasets. These datasets will include raw variables, and variables created from the raw variables as required for the analysis. Derived datasets will be created in SAS; all codes used to create derived datasets will be saved and validated. No ADaM or SDTM datasets will be produced.

[figure not shown]
3.3. Data Dictionary

A data dictionary is automatically generated within the Electronic Data Capture (EDC) based on the electronic Case Report Form (eCRF). The data dictionary has been exported from the EDC into a Microsoft® Excel worksheet. Any derived variables will be added to the data dictionary. The data dictionary will provide the following information: 1) raw data set variable name; 2) derived variable name; 3) description of the variable; 4) variable type/permissible entries; 4) allowance of not applicable entries; and 5) notes.

3.4. Missing Data

The eCRF is designed to ensure that no questions are left unanswered. If 'unknown' is selected, this will be included as such in the results and tabulated for all variables. Central tendencies will not be measured for continuous unknown data, only counts and percentages will be recorded.

In some cases, imputation of unknown variables may be conducted if the variable is to be used in calculations for another variable or analysis. For example, the eCRF allows some dates to be incomplete (i.e. day is unknown) if it is not available in the medical chart. This may impact accurate calculation of durations, resulting in an imputation needing to be made. If the day is missing, the date will be imputed as the 15th of the month, except in cases where this would lead to a negative duration, in which case the 1st or last day of the month will be used (whichever addresses the negative duration). No imputation will be made for missing month/year; these are classified as date unknown within the eCRF. All imputed values will be documented and presented as footnotes in the result tables.

4. Planned Analyses

The analyses detailed below will be performed to meet the project objectives. There will be two analysis populations specified for the analyses to be conducted:

- The **Effectiveness Population** consists of all eligible study eyes in the population except in instances when a patient has contributed both eligible eyes in the study, then only the eye that received the Xen-45 implant first will be selected; this eye will be presented in tables as the 'primary eye'. All results tables in the Effectiveness Population will include stratified results presenting data for the primary eye, as well as data on all included patient eyes (even if both eyes from a single patient are included).
- The **Safety Population** consists of all eligible study eyes in the population.

All results tables will be stratified by Xen-45 implant only, implant plus phacoemulsification, and total population. Sensitivity analyses will be conducted to assess study results in the 'second eye' (i.e. not the primary eye as described above), for patients where both eyes were included. The sensitivity analyses will focus on the tables conducted using the Effectiveness Population.

Categorical variables will be summarised by number and percentage of each response and will include number of unknown responses. Continuous variables will be summarised by mean, standard deviation, median, upper and lower quartiles, minimum and maximum values and proportion with unknown data.

[figure not shown]

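### The second-eye sensitivity analysis never shows the first eyes of the same bilateral patients, so it mixes eye order with patient type; a swap run and a paired display would separate them

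*SAP*

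**What the plan says.** SAP section 4 defines the Effectiveness Population with one eye per patient as the main presentation. Where both eyes are eligible, "then only the eye that received the Xen-45 implant first will be selected", and that eye is called the primary eye. The same section says that every effectiveness table also presents all included eyes, including both eyes of one patient. It then adds sensitivity analyses of results in the second eye, meaning "not the primary eye as described above), for patients where both eyes were included", focused on the effectiveness tables. All tables are further split by procedure (implant alone, implant with phacoemulsification, total).

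Three things are not planned: a table of first eyes restricted to bilateral patients, a within-patient comparison of first and second eyes, and an analysis in which the second eye takes the place of the first. Neither document states how many bilateral patients are expected.

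SAP section 4.4 limits each time point to eyes with data in the window and no Diamox on the day of the decision to implant.

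**The concern.** A sensitivity analysis on a selection rule is most useful when it changes the rule and keeps everything else fixed. Here the primary tables hold one eye from every patient, unilateral and bilateral. The second-eye tables hold only bilateral patients. Setting one beside the other changes the eye and the mix of patients together. If the results differ, the reader cannot tell whether eye order or patient type is responsible. If they look alike, the second-eye sample may be too small for that to mean much.

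What is at stake is the interpretation of a supplementary analysis. The primary estimate itself is not affected.

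**Working it through.** **Inputs.** Protocol section 14.1 gives these:
- "The MS-001 study enrolled 199 patients (218 study eyes", so 218 − 199 = 19 second eyes.
- "the study will aim to select 150 eyes to ensure obtaining a minimum of 60 eyes with at least 3 years of follow-up data", so a planned minimum of 60/150 = 40%.
- "it could be assumed that 30% of the eyes selected for this study have less than 3 years of follow-up data", so 70% retained, or 105 of 150 eyes.
- A projected mean reduction of "5.6 (± 6.32) mmHg, which was observed at Month 3".

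SAP section 2 words the target as a "minimum of 60 independent study eyes".

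**The plan's own figure.** Half-length = 1.96 × SD/√n = 1.96 × 6.32/√60 = 1.60 mmHg, so −5.6 ± 1.6 gives −7.2 to −4.0. This agrees with the protocol's "projected mean reduction afforded by a sample of 60 study eyes is -7.2 to -4.0 mmHg". With the t distribution the half-length is 1.63.

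**What the planned contrasts measure.** At one time point, let U be the mean change in unilateral patients, F and S the means in the first and second eyes of bilateral patients, and b the bilateral share of patients. Take both eyes as evaluable. The primary-eye mean is P = (1 − b)U + bF.

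- Second-eye table against primary table: S − P = (S − F) + (1 − b)(F − U). The first term is eye order; the second is patient type. On the MS-001 ratio b = 19/199 = 9.5%, so the patient-type difference enters with weight 0.905. If F and U differed by 3 mmHg (assumption) and eye order had no effect, the tables would still differ by 0.905 × 3 = 2.7 mmHg.
- All-eyes column against primary column: with second eyes as share s of all eyes, the difference is s(S − P). On the MS-001 ratio s = 19/218 = 8.7%. It is the same mixed contrast, diluted.
- Swap run against primary: the difference is b(S − F). Only eye order remains.

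**How many second eyes at Month 36.** Eyes with 3 years of data are taken as the Month 36 count, with first and second eyes retained equally.

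| Assumption | Second eyes in 150 | At 40% | At 70% | 95% half-length (mmHg) |
|---|---|---|---|---|
| MS-001 ratio | 150 × 19/218 = 13.1 | 5.2 | 9.2 | 7.85 (n = 5) to 4.86 (n = 9) |
| 20% of patients bilateral | 150 × 0.2/1.2 = 25 | 10 | 17.5 | 4.52 at n = 10 |
| 30% of patients bilateral | 150 × 0.3/1.3 = 34.6 | 13.8 | 24.2 | 2.67 at n = 24 |

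Half-length = t(0.975, n − 1) × 6.32/√n. For n = 5 it is 2.776 × 6.32/√5 = 7.85; for n = 9 it is 2.306 × 6.32/√9 = 4.86. If the 60 are independent eyes, the MS-001 ratio gives 60 × 19/199 = 5.7 second eyes. The split by procedure and the Diamox exclusion reduce these numbers further. Protocol section 9.2 has sites take an eligible second eye out of date order, which could raise the share above that in MS-001.

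**How much the rule could move the overall mean.** The shift is b(S − F). For an assumed 3 mmHg difference between second and first eyes it is 0.095 × 3 = 0.29 mmHg on the MS-001 ratio, 0.20 × 3 = 0.6 at 20% bilateral and 0.30 × 3 = 0.9 at 30%.

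**Precision of the swap contrast.** With 5 pairs among 60 patients and an assumed within-pair correlation of 0.5, the SD of the paired difference is 6.32 × √(2 × 0.5) = 6.32. The mean difference is then known to ±7.85 mmHg, and the rule's effect on the overall mean to ±7.85 × 5/60 = ±0.65 mmHg.

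**The case against.** The other side has several fair points.

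- A reader might infer that the second-eye run is the only check on the first-eye rule. It is not: section 4 of the SAP puts all eyes beside primary eyes in every effectiveness table, so a reader can see whether the point estimate moves. This stands, but that movement is s(S − P) and inherits the mixing shown above.
- A reader might infer that the second eyes come from a different patient group. They do not. Every patient who contributes a second eye also contributes a first eye to the Effectiveness Population, so they are a subset.
- The SAP says only that results in the second eye will be assessed. It does not claim to isolate eye order, and describing the eyes left out of the primary set is legitimate. This stands, and is a reason to keep those tables under a descriptive label.
- The argument from few eyes and the argument that the rule matters pull against each other. If second eyes are rare, the rule can hardly move the mean; if they are common, the second-eye sample is less sparse. This stands as a limit on importance. The mixing of eye order with patient type remains at any bilateral share.
- The swap run shares most of its eyes with the primary run, so it will look stable unless second eyes differ a great deal. The 1.6 mmHg half-length at n = 60 describes the swapped mean, not the first-versus-second contrast, which rests on the same few pairs. This stands, and is why the paired display is needed beside the swap.
- The wording does not wholly exclude a substitution reading. Clarification would settle that.

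**Conclusion.** The point holds as a cheap improvement. As naturally read, the second-eye analysis cannot separate eye order from bilateral status, because the first eyes of the same patients are not shown, and the all-eyes column does not resolve this.

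The numbers of second eyes (about 5 to 9 on the MS-001 ratio, about 10 to 24 if 20 to 30% of patients are bilateral) are assumptions, since the documents give no share for this study. They also assume equal retention of first and second eyes and an SD of 6.32 mmHg.

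A reader might go further and infer that the first-eye rule distorts the primary result. The documents do not support that: on the MS-001 ratio, an assumed 3 mmHg difference between second and first eyes shifts the mean by about 0.3 mmHg, well inside the planned half-length of 1.6 mmHg.

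**What to change.** In SAP section 4:

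1. State that the sensitivity analysis repeats the effectiveness tables with the second eye replacing the first in bilateral patients, and with all unilateral patients kept.
2. For bilateral patients with both eyes evaluable at the time point, add first eye, second eye and within-patient difference side by side, with the number of pairs.
3. Keep the stand-alone second-eye tables, labelled as descriptive.

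The cost is SAP wording and a re-run of existing table programs. No new data are needed, because both documents already have the eyes paired in the data capture system. The swapped set may lose a few patients whose second eye lacks Month 36 data; report how many. The paired contrast will still rest on few pairs, and the report should say so.
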